1.3 Schedule of Activities	Added COVID-19 testing.	Due to global COVID-19 restrictions, COVID-19 testing was added to the screening visit and prior to the duodenal biopsy procedure to ensure participant safety.

1 PROTOCOL SUMMARY

1.1 Synopsis

Protocol Title: A Gluten Challenge Study to Characterize Peripheral Blood and Intestinal Gluten-specific CD4+ T cell Subsets in Patients With Celiac Disease

Short Title: Gluten Challenge Study in Celiac Disease Patients

Acronym: Not applicable

Hypotheses, Objectives, and Endpoints:

Hypotheses are aligned with objectives in the Objectives and Endpoints table.

This study is to be conducted in male and female participants with celiac disease.

Primary Objectives	Primary Endpoints

- To determine the phenotypes of gliadin peptide/HLA-DQ2 multimer-positive CD4+ T cell subsets in the peripheral blood before and after gluten challenge and from duodenal biopsies after gluten challenge. Estimation: The percentages of α-gliadin and ω-gliadin-reactive CD4+ T cells expressing known activation and inhibitory receptors (including but not limited to: CD25 (IL-2R), CD95 (Fas), CD279 (PD-1), TGFβ1R, and IL-27R) will be estimated.
	
- α-gliadin and ω-gliadin-reactive CD4+ T cells

Overall Design:

Study Phase	Early Phase 1
Primary Purpose	Basic Science
Indication	Celiac Disease
Population	Participants with celiac disease
Study Type	Interventional
Intervention Model	Single Group This is a multi-site study.
Type of Control	No Treatment Control
Study Blinding	Unblinded Open-label
Masking	No Masking
Estimated Duration of Study	The Sponsor estimates that the study will require approximately 12 months from the time the first participant signs the informed consent until the last participant's last study-related telephone call or visit.

Number of Participants:

Approximately 15 participants will be allocated/randomized such that 15 evaluable participants complete the study as described in Section 9.9.

Intervention Groups and Duration:

Intervention Groups	Intervention Details						
	Intervention Group Name	Intervention	Dose Strength	Dose Frequency	Route of Admin.	Regimen/Treatment Period	Use
All participants	Gluten	4 g	Twice daily	Oral	Daily for 13 days	Challenge agent	
Total Number	1						
Duration of Participation	Each participant will participate in the study for approximately 8 weeks from the time the participant signs the Informed Consent Form through the final contact. After a screening period of up to 28 days, each participant will be receiving assigned intervention for 13 days. After the end of treatment each participant will be followed for 14 days.						

Study Governance Committees:

Steering Committee	No
Executive Oversight Committee	No
Data Monitoring Committee	No
Clinical Adjudication Committee	No
Study governance considerations are outlined in Appendix 1.	

Study Accepts Healthy Volunteers: No

A list of abbreviations used in this document can be found in Appendix 11.

1.2 Schema

The study design is depicted in [Figure 1](#).

[figure not shown]

Figure 1 Study Diagram

1.3 Schedule of Activities (SoA)

Study Period	All Panels/Periods						
	Screening	Pre-dose	Intervention			Post-study	Notes
Scheduled Day	Screening (up to -28 days)	Day 1 Pre-dose	Day 1	Day 6	Day 13	Day 14 (+/- 1 day)	Post-study (14 days after last gluten administration)
Administrative Procedures							
Informed Consent	X						
Informed Consent for Future Biomedical Research	X						
Assignment of Screening Number	X						
Participant Identification Card	X						
Inclusion/Exclusion Criteria	X	X					Recheck clinical status before start of gluten challenge
Medical History	X						Includes usage of drugs, alcohol, and tobacco
Prior/Concomitant Medication Review	X	X	X	X		X	
Assignment of Treatment/Randomization Number		X					
Gluten Administration/Dispensing			X-----X				Gluten will be administered daily from Day 1 to Day 13. In the event that Day 14 procedures are conducted on Day 13, gluten intended for Day 13 will not be consumed.
Participant Gluten Consumption Log			X-----X				Participants will complete this log daily.
Safety Procedures							
Full physical examination	X	X			X		Pre-dose will be targeted PE
Height	X						
Weight	X	X			X	X	
Vital Signs (BP, HR, RR)	X	X			X	X	

Study Period	All Panels/Periods						
	Screening	Pre-dose	Intervention			Post-study	Notes
Scheduled Day	Screening (up to -28 days)	Day 1 Pre-dose	Day 1	Day 6	Day 13	Day 14 (+/- 1 day)	Post-study (14 days after last gluten administration)
Body Temperature	X	X				X	X
12-lead ECG	X						
Serum β -Human Chorionic Gonadotropin (β -hCG; WOCBP only)	X						
Urine β -Human Chorionic Gonadotropin (β -hCG; WOCBP only)		X				X	
Serum FSH - (postmenopausal women only)	X						
Blood for HLA Genotyping for Celiac Disease	X						Results from previous testing may be used in lieu of genotyping at screening
Anti-tTg, HIV, hepatitis B and C screen	X						
UDS	X						Screening UDS is mandatory, any additional UDS are conducted per site SOP
COVID-19 Testing	X					X	COVID-19 nasal swab test or blood test, per local practice, if deemed possible/allowed based on test capacity, and according to local health practice. Testing prior to the Day 14 duodenal biopsy may be done within 2 to 3 days prior to the procedure per the investigator's discretion. Result must be negative for duodenal biopsy to be performed.
Hematology	X					X	
Urinalysis	X					X	

Study Period	All Panels/Periods						
	Screening	Pre-dose	Intervention			Post-study	Notes
Scheduled Day	Screening (up to -28 days)	Day 1 Pre-dose	Day 1	Day 6	Day 13	Day 14 (+/- 1 day)	Post-study (14 days after last gluten administration)
Chemistry	X					X	
CDSD	X	X-----X					Participants will complete the CDSD daily.
AE/SAE review	X	X	X	X	X	X	
Pharmacodynamics							
Blood for Serum Cytokine/Chemokine Assay		X		X		X	
Blood for PBMC		X		X		X	
Duodenal Biopsy						X	
Biomarkers							
Blood for Genetic Analysis		X					Collect predose from enrolled participants only – See Section 8.8
AE=adverse event; BP=blood pressure; CDSD=Celiac Disease Symptom Diary; ECG=electrocardiogram; FSH=follicle-stimulating hormone; hCG=human chorionic gonadotropin; HLA=human lymphocyte antigen; HR=heart rate; PBMC=peripheral blood mononuclear cells; PE=physical examination; RR=respiratory rate; SAE=serious adverse event; UDS=urine drug screen; WOCBP=women of childbearing potential							

2 INTRODUCTION

2.1 Study Rationale

The objective of this experimental medicine study is to profile cell surface receptors on blood and intestinal gluten-specific CD4+ cells from patients with CeD to inform the development of novel therapies for celiac disease.

2.2 Background

Celiac disease is an enteropathy of the small intestine triggered by ingestion of gluten present in wheat (gliadin), rye (secalin), and barley (hordein). It is one of the most common immune-mediated diseases, affecting an estimated 10 million people globally, with a prevalence of 0.5-1% which is predicted to increase over time. It is a malabsorptive disease characterized by GI symptoms (diarrhea, weight loss) and vitamin deficiencies (iron, vitamin D), leading to anemia and osteoporosis. CeD is diagnosed by the presence of antibodies to tTG and characteristic pathologic changes on duodenal biopsies. The only current management option for CeD is strict, lifelong adherence to a GFD; however, unintentional exposure to gluten through food contamination is common, which may lead to persistent disease over time. In addition, gluten-free food options can be scarce, expensive, and low in key nutrients, and patient anxiety in social situations involving food is common. There is a high unmet need for CeD treatments beyond GFD, and multiple agents are being studied for the treatment of CeD in Phase 2 clinical trials, targeting both immune- and non-immune mediated mechanisms [Wungjiranirun, M., et al 2016].

Proline-rich gliadin peptides derived from gluten are deamidated in intestinal submucosa by type 2 tTG, which then bind with high affinity to HLA-DQ2.5/DQ8 (~90%/~10% CeD patients, respectively) on antigen presenting cells. These HLA-gliadin complexes bind to specific gluten-specific T cell receptors expressed by CD4+ T cells in the lamina propria, differentiating them towards a pro-inflammatory Th1 phenotype, producing cytokines such as IFN- γ , IL-21, and TNF α . Within the inflammatory lesion, B cells act as antigen presenting cells (APCs) for gliadin-specific T cells and differentiate into plasma cells producing high affinity anti-TTG Abs, whose pathogenic significance are not clear, but function as a biomarker for disease diagnosis and recent gluten exposure. Activated intraepithelial CD8 T cells induce further mucosal damage [Jabri, B. 2017].

The HLA-DQ2.5 restricted, gluten-specific Th1 response in CeD is largely driven by a few overlapping immunodominant gliadin peptides. Multiple studies have confirmed α -gliadin 57-73 (Q65E) as a dominant T cell epitope in CeD [Anderson, R. P., et al 2000]. A follow up epitope mapping study systematically profiled gliadin peptide libraries consisting of over 2500 20-aa oligopeptides and identified ω -gliadin W03-E7 as an additional immunodominant peptide [Tye-Din, J. A., et al 2010]. Regulatory T cells (Tregs) play an important role in maintaining immune tolerance. Treg subsets, including FOXP3+ Tregs (CD4+CD25+IL-127 low) and IL-10 producing Tr1 T cells (CD4+CD49b+LAG3+), can be generated in vitro and are being studied in cellular therapy clinical trials for organ transplantation and T1DM.

2.3 Benefit/Risk Assessment

Participants in this clinical study will not receive direct benefit from participation.

Risks anticipated for participants in this trial are those related to the gluten challenge, venipuncture and biopsy procedures.

Additional details regarding specific benefits and risks for participants participating in this clinical study may be found in the accompanying informed consent documents.

3 HYPOTHESES, OBJECTIVES, AND ENDPOINTS

Hypotheses are aligned with objectives in the Objectives and Endpoints table.

This study is to be conducted in male and female participants with celiac disease.

Objectives	Endpoints
Primary	

To determine the phenotypes of gliadin peptide/HLA-DQ2 multimer-positive CD4+ T cell subsets in the peripheral blood before and after gluten challenge and from duodenal biopsies after gluten challenge. Estimation: The percentages of α-gliadin and ω-gliadin-reactive CD4+ T cells expressing known activation and inhibitory receptors (including but not limited to: CD25 (IL-2R), CD95 (Fas), CD279 (PD-1), TGFβ1R, and IL-27R) will be estimated.	
α-gliadin and ω-gliadin-reactive CD4+ T cells
Secondary	

None	
Exploratory	

To estimate the frequency, phenotype, and function of effector IFN-γ-producing gluten-specific CD4+ T cells (Teff) in the peripheral blood before and after gluten challenge.	
effector IFN-γ-producing gluten-specific CD4+ T cells (Teff)

Objectives	Endpoints

 To characterize individual single-cell gene expression to define T cell receptor sequences as well as novel activation and inhibitory receptors in blood (pre- and post-gluten challenge) and post-gluten challenge duodenal biopsies using single cell RNA sequencing (scRNA-Seq). 	
 single cell RNA sequencing (scRNA-Seq).

 To determine the relationship between severity of histologic damage on duodenal biopsy, celiac disease symptoms, and the quantity and quality of gluten-specific CD4+ T cell responses after gluten challenge. 	
 Histology, CDSD, gluten-specific CD4+ T cells

 To estimate the frequency, phenotype, and function of blood and duodenal gluten-specific CD4+ regulatory T cells (Treg) induced after in vitro treatment with experimental compounds. 	
 gluten-specific CD4+ regulatory T cells (Treg)

 To estimate the frequency, phenotype, and function of effector IFN-γ-producing gluten-specific CD4+ T cells (Teff) after in vitro treatment with experimental compounds. 	
 effector IFN-γ-producing gluten-specific CD4+ T cells (Teff)

 To estimate the levels of cytokines and chemokines in serum before and after gluten challenge 	
 Serum cytokines and chemokines

 To explore the relationship between genetic variation and response to the treatment(s) administered, and mechanisms of disease. Variation across the human genome may be analyzed for association with clinical data collected in this study. 	
 Germline genetic variation

4 STUDY DESIGN

4.1 Overall Design

This is a multi-site, open-label gluten challenge study to characterize peripheral blood and intestinal gluten-specific CD4+ T cell subsets in patients with CeD. Participants will receive 8 g gluten daily for 13 consecutive days. Blood samples will be taken at pre-dose, Day 6, and Day 14. Duodenal biopsy samples will also be collected on Day 14. Participants will complete a symptom diary as described in the SoA.

Specific procedures to be performed during the study, as well as their prescribed times and associated visit windows, are outlined in the SoA in Section 1.3. Details of each procedure are provided in Section 8.

Because it is a Phase 1 assessment of a gluten challenge in humans, and the pharmacodynamic and safety profiles of a gluten challenge are being evaluated, this protocol is written with flexibility to accommodate the inherent dynamic nature of Phase 1 clinical studies. Refer to Section 8.11.6 for examples of modification permitted within the protocol parameters.

4.2 Scientific Rationale for Study Design

Gliadin-specific CD4+ T cells are infrequent in the blood above background staining by flow cytometry in patients with CeD on a GFD [Raki, M., et al 2007]. Gliadin-specific CD4+ T cells may be identified by flow cytometry using MHC-gliadin tetramers. After the first three days of a gluten challenge, gliadin-specific T cells are detectable in the blood on day 6 after initial challenge and can therefore be readily identified [Raki, M., et al 2007]. Gliadin peptide mixtures can stimulate an IFN- γ enzyme-linked immunospot (ELISPOT) response from peripheral blood T cells after gluten challenge [Tye-Din, J. A., et al 2010]. Gliadin-specific T cells may also be isolated at ~10-100x higher frequencies from duodenal biopsies after gluten challenge [Bodd, M., et al 2013]. A traditional gluten challenge used in clinical practice for the diagnosis of CeD may last from 2 to 8 weeks. A biomarker study assessing histologic responses at 3 and 14 days after gluten challenge determined that histologic changes were more pronounced at 14 days at both dosage levels [Lefluer, D., et al 2013]; therefore, a 13 day gluten challenge is proposed in order to maximize the feasibility of obtaining immune cells in the blood and duodenum on Day 14, as well as to adequately replicate the inflammatory milieu for scRNA-Seq analysis. Polyclonal gliadin-specific T cell cultures and monoclonal gliadin-specific T cell lines from patients will also be generated for long-term use in the laboratory using established protocols. These assays will be utilized to analyze gliadin-specific T cells from patients after gluten challenge.

4.2.1 Rationale for Endpoints

4.2.1.1 Safety Endpoints

The safety and tolerability of gluten administration and procedures during this study will be evaluated by clinical assessment of adverse experiences and other safety measurements. Summary statistics for laboratory safety tests and/or vital signs may also be computed, as deemed clinically appropriate.

4.2.1.2 Pharmacodynamic Endpoints

Patient responses to gluten challenge will be monitored by symptom assessment using the CDSD and by histologic scoring of duodenal biopsies.

4.2.1.3 Planned Exploratory Biomarker Research

4.2.1.3.1 Planned Genetic Analysis

Genetic variation may impact a participant's response to therapy, susceptibility to, severity, and progression of disease. Variable response to therapy may be due to genetic determinants that impact drug absorption, distribution, metabolism, and excretion; mechanism of action of the drug; disease etiology; and/or molecular subtype of the disease being treated. Therefore, where local regulations and IRB/IEC allow, a sample will be collected for DNA analysis from consenting participants.

DNA samples may be used for research related to the study intervention(s), the disease under study, or related diseases. They may also be used to develop tests/assays including diagnostic tests related to the disease under study, related diseases, and study intervention(s). Genetic research may consist of the analysis of 1 or more candidate genes, the analysis of genetic markers throughout the genome, or analysis of the entire genome. Analysis may be conducted if it is hypothesized that this may help further understand the clinical data.

The samples may be analyzed as part of a multi-study assessment of genetic factors involved in the response to understand study disease or related conditions.

4.2.1.4 Future Biomedical Research

The Sponsor will conduct future biomedical research on specimens for which consent was provided during this study. This research may include genetic analyses (DNA), gene expression profiling (RNA), proteomics, metabolomics (serum, plasma), and/or the measurement of other analytes, depending on which specimens are consented for future biomedical research.

Such research is for biomarker testing to address emergent questions not described elsewhere in the protocol (as part of the main study) and will only be conducted on specimens from appropriately consented participants. The objective of collecting/retaining specimens for future biomedical research is to explore and identify biomarkers that inform the scientific understanding of diseases and/or their therapeutic treatments. The overarching goal is to use

such information to develop safer, more effective drugs/vaccines, and/or to ensure that participants receive the correct dose of the correct drug/vaccine at the correct time. The details of this future biomedical research are presented in Appendix 6.

4.3 Justification for Dose

A biomarker study assessing histologic responses at 3 and 14 days after both low-dose (3 g/day) and high-dose (7.5 g/day) gluten challenges determined that histologic changes were more pronounced at 14 days at both dosage levels [Leffler, D., et al 2013]. Another biomarker study determined that a 5.7 g/day gluten challenge administered over 14 days resulted in significant increases in circulating gluten-specific T cells and intraepithelial lymphocytes on duodenal biopsy, but did not fully establish significant mucosal architectural changes in the majority of patients [Sarna, V. K., et al 2018]. An 8 g/day, 13-day gluten challenge is proposed in order to maximize the feasibility of obtaining immune cells in the blood and duodenum and to replicate the inflammatory milieu for scRNA-Seq analysis.

As this is a Phase 1 assessment of a gluten challenge in humans, and the pharmacodynamic and safety profiles of a gluten challenge are being evaluated, modifications to the dosing regimen or study procedures may be required to achieve the scientific goals of the study objectives and/or to ensure appropriate safety monitoring of the study participants. Details of allowed modifications are provided in Section 8.11.6.

4.4 Beginning and End of Study Definition

The overall study begins when the first participant signs the ICF. The overall study ends when the last participant completes the last study-related telephone-call or visit, withdraws from the study, or is lost to follow-up (ie, the participant is unable to be contacted by the investigator).

A study may be paused during review of newly available preclinical/clinical safety, PK, pharmacodynamic, efficacy, or biologic data or other items of interest, prior to a final decision on continuation or termination of the study. It may be necessary to keep the study open for gathering/reviewing of additional supportive data to optimally complete the objective(s) of the study. If necessary, the appropriate amendment(s) to the protocol and/or appropriate communication(s) will be generated. The overall study end will then not be identified until the Sponsor has made the decision to end the study following this review period. The Competent Authority(ies) and Institutional Review Board(s)/Independent Ethics Committee(s) [IRB(s)/IEC(s)] will be apprised of the maximum duration of the study beyond the last participant out and the justification for keeping the study open.

4.4.1 Clinical Criteria for Early Study Termination

There are no prespecified criteria for terminating the study early.

5 STUDY POPULATION

Male/Female participants with biopsy-proven CeD between the ages of 18 and 70 years (inclusive) will be enrolled in this study.

Prospective approval of protocol deviations to recruitment and enrollment criteria, also known as protocol waivers or exemptions, is not permitted.

5.1 Inclusion Criteria

To be eligible for inclusion in this study, the participant must:

1. Participant must have documented diagnosis with CeD by duodenal/jejunal biopsy at least 6 months prior to entrance into the study.
2. Participant must be on a GFD for at least the past 12 months.

Demographics

3. Participant is male or female.
4. Participant is from 18 years to 70 years of age inclusive, at the time of signing the informed consent.

Female Participants

5. A female participant is eligible to participate if she is not pregnant or breastfeeding, and at least one of the following conditions applies:
 - Is not a WOCBP
 - OR
 - Is a WOCBP and using an acceptable contraceptive method, or be abstinent from heterosexual intercourse as their preferred and usual lifestyle (abstinent on a long term and persistent basis), as described in Appendix 5 during the intervention period and for at least 14 days after the last dose of study intervention. The investigator should evaluate the potential for contraceptive method failure (ie, noncompliance, recently initiated) in relationship to the first dose of study intervention.
 - Additional requirements for pregnancy testing during and after study intervention are located in Appendix 2.
 - The investigator is responsible for review of medical history, menstrual history, and recent sexual activity to decrease the risk for inclusion of a woman with an early undetected pregnancy.

Informed Consent

6. The participant (or legally acceptable representative if applicable) provides written informed consent/assent for the study. The participant may also provide consent/assent for future biomedical research. However, the participant may participate in the main study without participating in future biomedical research.

Diagnostic Assessments

7. Must be HLA-DQ2.5 positive, assessed at screening. If participants have already been genotyped, results from previous testing may be used in lieu of genotyping at screening.
8. Has anti-tTG <2x ULN as measured by serology.

Medical Condition

9. Be judged to be in good health based on medical history, physical examination (including a targeted neurological exam), VS measurements and ECG performed prior to treatment allocation.
10. Have a BMI 18-35 kg/m², inclusive. See Section 8.3.1 for criteria on rounding to the nearest whole number. BMI = weight (kg)/height (m)².

Other Inclusions

11. Have a negative urinary screen for illicit drugs at screening.
12. Understands study procedures and is willing to comply with trial restrictions (see Section 5.3 for a summary of trial restrictions).
13. Be judged to be in good health based on laboratory safety tests obtained at screening. Appendix 2 provides a table of laboratory safety tests to be performed, and Appendix 10 provides an algorithm for the assessment of out of range laboratory values.

5.2 Exclusion Criteria

The participant must be excluded from the study if the participant:

Medical Conditions

1. Has any chronic active GI disease (eg, clinically active CeD despite being on GFD for past 12 months, Crohn's disease, ulcerative colitis, lymphocytic colitis). Inactive, stable/well-treated lactose intolerance, FODMAP intolerance, GERD, and IBS are allowed.

2. Has clinically active endocrine, gastrointestinal (other than CeD), cardiovascular, hematological, hepatic, immunological, renal, respiratory, genitourinary, or major neurological (including stroke and chronic seizures) abnormalities or diseases. Participants with a remote history of uncomplicated medical events or stable medical diseases with no symptoms and stable treatment for the past >3 months may be enrolled in the study at the discretion of the investigator.
3. Is mentally or legally incapacitated, has significant emotional problems at the time of prestudy (screening) visit or expected during the conduct of the study or has a history of clinically significant psychiatric disorder within the last 5 years. Participants who have had situational depression may be enrolled in the study at the discretion of the investigator.
4. Participant has an eGFR ≤ 80 mL/min/1.73 m² at the screening visit based on the Cockcroft-Gault (CG) equation below:

Cockcroft-Gault Equation:

$$\text{ClCr} = \frac{(140 - \text{age[yr]})(\text{body wt [kg]})}{(72)(\text{serum creat [mg/dL]})}$$

$$(72)(\text{serum creatinine [micromol/L]} \times 0.0113)$$

When creatinine is measured in micromole/litre, use this formula:

$$\text{ClCr} = \frac{(140 - \text{age[yr]})(\text{body wt[kg]})}{(72)(\text{serum creatinine [micromol/L]} \times 0.0113)}$$

For females, multiple the result by 0.85.

At the discretion of the investigator a measured creatinine clearance, as determined by a 24-hour urine collection, may be used in place of, or in conjunction with, the estimate of the creatinine clearance.

Participants who have a measured creatinine clearance of up to 10% below 80 mL/min may be enrolled in the study at the discretion of the investigator.

5. Has a history of significant multiple and/or severe allergies (eg, food, drug, latex allergy), or has had an anaphylactic reaction or systemic allergic reaction to prescription or non-prescription drugs or food.
6. Subject has a history of severe acute symptomatic reactions to sporadic gluten ingestion.
7. Is positive for hepatitis B surface antigen, hepatitis C antibodies or HIV.
8. Had major surgery, donated or lost 1 unit of blood (approximately 500 mL) within 4 weeks prior to the prestudy (screening) visit.

Prior/Concomitant Therapy

9. Is on Coumadin™ or other anticoagulants.
10. Is unable to refrain from or anticipates the use of systemic anti-inflammatory, immunosuppressive, or immunomodulatory medications, which may include ibuprofen > 2400 mg/day, naproxen >750 mg/day, prednisone >10 mg/day, or methylprednisolone > 8 mg/day, within 48 hours prior to the start of and throughout the entire gluten challenge.

Prior/Concurrent Clinical Study Experience

11. Has participated in another investigational study within 4 weeks (or 5 half-lives, whichever is greater) prior to the prestudy (screening) visit. The window will be derived from the date of the last visit in the previous study.

Diagnostic Assessments

12. Has a QTc interval \geq 470 msec (for males) or \geq 480 msec (for females).

Other Exclusions

13. Is under the age of legal consent.
14. Consumes greater than 3 glasses of alcoholic beverages (1 glass is approximately equivalent to: beer [354 mL/12 ounces], wine [118 mL/4 ounces], or distilled spirits [29.5 mL/1 ounce]) per day. Participants who consume 4 glasses of alcoholic beverages per day may be enrolled at the discretion of the investigator. All alcoholic beverages must be gluten free.
15. Is a regular user of any illicit drugs or has a history of drug (including alcohol) abuse within approximately 6 months. Participants must have a negative UDS at screening.
16. Presents any concern by the investigator regarding safe participation in the study or for any other reason the investigator considers the participant inappropriate for participation in the study.
17. Is or has an immediate family member (eg, spouse, parent/legal guardian, sibling, or child) who is investigational site or Sponsor staff directly involved with this study.

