6.5 Concomitant Therapy

Medications or vaccinations specifically prohibited in the exclusion criteria are not allowed during the ongoing study. If there is a clinical indication for any medications or vaccinations specifically prohibited, discontinuation from study intervention may be required. The investigator should discuss any questions regarding this with the Sponsor Clinical Director. The final decision on any supportive therapy rests with the investigator and/or the participant's primary physician. However, the decision to continue the participant on study intervention requires the mutual agreement of the investigator, the Sponsor, and the participant.

At the investigator's discretion, participants may self-administer anti-nausea or anti-diarrheal medications (over the counter or prescribed by their own physician) according to the product label as needed. These medications will be recorded.

Listed below are specific restrictions for concomitant therapy:

Systemic anti-inflammatory, immunosuppressive, or immunomodulatory medications, which may include ibuprofen > 2400 mg/day, naproxen >750 mg/day, prednisone >10 mg/day, or methylprednisolone > 8 mg/day.

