8.1.5 Prior and Concomitant Medications Review

8.1.5.1 Prior Medications

The investigator or qualified designee will review prior medication use, including any protocol-specified washout requirement, and record prior medication taken by the participant within 3 months before starting the study.

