8.11.1 Screening

Up to approximately 4 weeks prior to intervention allocation, potential participants will be evaluated to determine that they fulfill the entry requirements as set forth in Section 5.

Participants may be rescreened after consultation with the Sponsor. Rescreening should include all screening procedures listed in the SoA, including consent review. Rescreen procedures cannot be conducted the day prior to intervention allocation.

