9.4 Analysis Endpoints

Primary Endpoints

- Percentage of α -gliadin and ω -gliadin-reactive CD4+ T cells expressing known activation and inhibitory receptors (including but not limited to: CD25 (IL-2R), CD95 (FasR), CD279 (PD-1), TGF β 1R, and IL-27R)) in the peripheral blood before and after gluten challenge and from duodenal biopsies after gluten challenge.

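### One 48-hour look-back for all systemic immune-acting drugs does not clear long-acting agents before a T-cell phenotype is measured, and the low-dose steroid rule is unclear

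*Combined protocol and SAP*

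**What the plan says.** Criterion 10 in section 5.2 excludes a candidate who cannot avoid, or expects to need, a systemic drug from any of three classes (anti-inflammatory, immunosuppressive, immunomodulatory) "within 48 hours prior to the start of and throughout the entire gluten challenge". No class has its own interval. The doses are attached loosely: "immunosuppressive, or immunomodulatory medications, which may include ibuprofen > 2400 mg/day", followed by limits for naproxen, prednisone (above 10 mg/day) and methylprednisolone (above 8 mg/day).

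Four other places bear on the point:

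- Section 6.5 repeats the list with the same wording and adds: "Medications or vaccinations specifically prohibited in the exclusion criteria are not allowed during the ongoing study".
- Section 8.11.1 places screening "Up to approximately 4 weeks prior to intervention allocation", which is an upper limit with no lower one.
- Section 8.1.5.1 has the site review prior drug use, "including any protocol-specified washout requirement, and record prior medication taken by the participant within 3 months before starting the study".
- Criterion 2 excludes clinically active immunological disease, but people with "stable medical diseases with no symptoms and stable treatment for the past >3 months may be enrolled in the study" at the investigator's discretion.

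The primary endpoint in section 9.4 is the percentage of gliadin-reactive CD4+ T cells that carry activation and inhibitory receptors, "in the peripheral blood before and after gluten challenge and from duodenal biopsies after gluten challenge".

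**The concern.** The endpoint is the activation state of T cells, and immunosuppressants and immunomodulators are taken to alter immune-cell behaviour. For a short-acting NSAID, 48 hours may well be enough. For an agent with a half-life of days or weeks it is not, and a drug given at long intervals can be last dosed before the window without triggering criterion 10 at all.

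The design has limited means of noticing. Duodenal tissue is taken only after challenge, so a residual drug effect there has no within-person reference. In blood, a drug that wears off between pre-dose and Day 14 moves together with the gluten effect, and there is no unchallenged group to separate them. The Per-Protocol definition in section 9.5 allows exclusion for important deviations, but a participant who met criterion 10 as written has not deviated from it.

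The dose wording is a separate problem. In a multi-site study, two sites could read it differently and enrol different people.

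**Working it through.** **The plan's own figure.** Table 3 gives the half-width of the 95% confidence interval at n = 15. The formula is t(0.975, 14) × SD / √15, with t = 2.1448, so the multiplier is 0.5538. At SD 10 this gives 5.538, as printed, and all 21 rows reproduce. Table 3 is not in dispute.

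**What 48 hours and 28 days cover.** With first-order elimination the fraction left after time t at half-life h is 2^(−t/h). Five half-lives leave 1/32 = 3.1%.

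- 48 h / 5 = 9.6 h is the longest half-life for which 48 hours reaches 5 half-lives.
- If section 6.5 is read to run from consent and screening lasts the full 28 days, 28 / 5 = 5.6 days is the longest half-life covered. A shorter screening covers less.

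**Drug left at the two blood times.** Half-lives of 3, 14 and 21 days are assumptions; the documents give none. Day 14 is 13 days after Day 1, so t is 2 and 15 days for a last dose 48 hours before Day 1, and 28 and 41 days for a last dose 28 days before.

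| Assumed half-life | Stopped 48 h before: Day 1 / Day 14 | Stopped 28 d before: Day 1 / Day 14 | 5 half-lives |
|---|---|---|---|
| 3 d | 63% / 3% | 0.2% / 0.01% | 15 d |
| 14 d | 91% / 48% | 25% / 13% | 70 d |
| 21 d | 94% / 61% | 40% / 26% | 105 d |

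These are drug levels, not effects on receptor expression. The 48-hour column is the worst case that criterion 10 alone permits. At an assumed 21 days, 5 half-lives (105 days) also exceed the roughly 90 days of medication history that section 8.1.5.1 asks for.

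**Effect of one exposed participant on a mean of 15.** The shift d is assumed. The mean moves by d/15, and the expected SD becomes √(SD² + d²/15), so the half-width widens as well.

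At SD 10:

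- d = 10: mean moves 0.67; half-width 0.5538 × 10.33 = 5.72
- d = 20: mean moves 1.33; half-width 0.5538 × 11.25 = 6.23; ratio 1.33 / 6.23 = 21%
- d = 30: mean moves 2.0; half-width 0.5538 × 12.65 = 7.00

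At SD 5 with d = 20: √(25 + 400/15) = 7.19, half-width 3.98, ratio 1.33 / 3.98 = 33%.

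**The steroid wording.** Under one reading all systemic corticosteroids are barred and the doses are examples. Under the other, only doses above the limits are barred. Section 6.5 repeats the text and does not choose between them.

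**The case against.** The strongest reply is that the exposed group is small and the harm is assumed. Criteria 1 and 2 remove active gastrointestinal and immunological disease, inclusions 9 and 13 require good health, criterion 16 lets the investigator refuse anyone, eligibility is rechecked before dosing, and three months of medication are recorded. Section 6.5 probably reaches back to consent, which makes the 91% and 94% figures unlikely in practice. The analysis is descriptive, tests no hypothesis, and reports medians and ranges beside means. A 20-point shift at SD 5 is four standard deviations and would show in a listing of 15. Numeric steroid limits also have little purpose unless they mark the barred doses, and a steady low dose affects both blood samples alike.

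Most of this stands and limits the weight of the point. It does not supply a washout: none of these provisions sets an interval longer than 48 hours before Day 1, apart from whatever length screening happens to have. At SD 10 the same shift is two standard deviations and need not stand out.

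A reader might also infer that the protocol breaks its own standard, because criterion 11 excludes participation in another investigational study "within 4 weeks (or 5 half-lives, whichever is greater) prior to the prestudy (screening) visit". The documents do not support that. Criterion 11 applies whatever the agent was, and it counts from the last visit of the earlier study back to screening, not from last dose to Day 1. It is not a T-cell washout rule; it shows only that the protocol uses half-lives elsewhere.

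**Conclusion.** The point holds as a cheap improvement. As written, criterion 10 permits carry-over of a long-acting immunosuppressant or immunomodulator into the primary endpoint, and no other section reliably closes the gap. The low-dose steroid rule can be read two ways.

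The size is probably modest. One participant shifted by an assumed 20 points moves the mean by about a fifth of the interval half-width at SD 10 and about a third at SD 5. Half-lives and shift size are assumptions, and the documents give no exposure rate, so no probability that an exposed person enrols is offered. A reader might go further and conclude that the phenotype results would be unreliable, or that exposed participants are to be expected. Nothing in the documents supports either. Sample size and Table 3 are unaffected.

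**What to change.** Amend criterion 10 in section 5.2, and section 6.5 to match:

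1. For NSAIDs, keep 48 hours and the listed dose limits.
2. For systemic immunosuppressants and immunomodulators, require at least 5 half-lives from last dose to Day 1, with a 4-week floor if the sponsor wishes, and no use until the Day 14 samples have been taken.
3. State plainly whether corticosteroids at or below the listed doses are allowed. If they are, require a stable dose from screening.
4. In section 8.1.5.1, record the last-dose date of the drugs in item 2 without the 3-month limit.

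Candidates who need such a drug should be excluded, not taken off treatment.

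The cost is one amendment to three sections and a small loss of eligible candidates. That loss cannot be quantified, because the documents give no rate of use and no screen-failure rate. Sample size, visits, assays and the planned summaries stay as they are.
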